## Study synopsis.

	
weeks follow-up visit. New lesions which were not existed in baseline will not be counted.
 

• Percentage of subjects that demonstrate a 26-50% in reduction in actinic keratoses lesion count 3 months after the final treatment.

• Percentage of subjects that demonstrate a 51-75% in reduction in actinic keratoses lesion count 3 months after the final treatment.

• Percentage of subjects that demonstrate more than 76% in reduction in actinic keratoses lesion count 3 months after the final treatment.

• Subjects' satisfaction assessed at the final follow-up visit (based on the subject experience questionnaire which includes 3 questions relating to treatment results, treatment experience and treatment expectations) graded on a score of 1- 5; 1 being not satisfied and 5 being very satisfied).

Safety Endpoints	

• Procedure related AEs

• Subject subjective downtime assessment - defined as the period of time following the procedure during which the subject felt unable/unwilling to go out in public due to skin reactions. The assessment will be recorded by the subject using the Subject Subjective Downtime Assessment following each treatment and will be collected at the site at the follow-up visits up to 4weeks FU following treatment 3 (third treatment).

• Procedure related pain by the subjects using VAS for pain of 0-10 where a higher score indicates greater pain.

## Study Analysis Plan

### Study Design and Objectives

This is a single-center, prospective, open label study with a before-after study design. The study is designed to evaluate the efficacy and safety of treating AKs of the scalp and/or face using the Tixel device.

### Study Endpoints

#### Primary efficacy endpoint

The overall mean percentage reduction in AK lesion count performed by the investigator manually, confirmed and documented using photograph images taken at baseline and at 12 weeks follow-up visit (before and after marking the present actinic keratoses using a washable eyeliner) calculated as the relative change from baseline at 12 weeks. New lesions which were not existed in baseline will not be counted.

#### Secondary efficacy endpoints

- The mean change in actinic keratoses lesion count, performed by the investigator manually, confirmed and documented using photographic images, from baseline at 4 and 12 weeks follow-up visit.
- The overall mean percentage reduction in AK lesion count performed by the investigator manually, confirmed and documented using photograph images taken at baseline and at 4 weeks follow-up visit (before and after marking the present actinic keratoses using a washable eyeliner) calculated as the relative change from baseline at 4 weeks. New lesions which were not existed in baseline will not be counted

## Study synopsis.

- Percentage of subjects that demonstrate a 26-50% in reduction in actinic keratoses lesion count 3 months after the final treatment.
- Percentage of subjects that demonstrate a 51-75% in reduction in actinic keratoses lesion count 3 months after the final treatment.
- Percentage of subjects that demonstrate more than 76% in reduction in actinic keratoses lesion count 3 months after the final treatment.
- Subject satisfaction assessment

### **Safety Endpoints**

- Procedure related AEs

- Subject subjective downtime assessment - defined as the period of time following the procedure during which the subject felt unable/unwilling to go out in public due to skin reactions.

- Procedure related pain by the subjects using VAS for pain of 0-10 where a higher score indicates greater pain.

### **Study Hypothesis**

In this study we will test the following hypothesis:

- Mean reduction in AKs lesion count 3 months after the final treatment will be at least 50%.

### **Sample Size Estimation**

When the sample size is 20, a two-sided 95% confidence interval for a single mean will extend 8 from the observed mean, assuming that the standard deviation is known to be 20 and the confidence interval is based on the large sample z statistic.

If the expected rate is 58% the lower bound of the 95% confidence interval will be 50%.

A result of 58% will ensure with 95% level of confidence that the true percentage is not less than 50%.

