## **Statistical Analysis**

### **General Considerations**

Baseline demographic and other baseline characteristics, together with safety analyses will be performed on all enrolled subjects. Baseline values are defined as the last valid value prior to first treatment.

Statistical analyses of safety and secondary efficacy will be mainly descriptive in nature. Continuous variables will be summarized by a mean, standard deviation, minimum, 25th percentile median 75th percentile and maximum. Categorical variables by a count and percentage. Where confidence limits are appropriate, a two-sided 95% confidence interval will be constructed.

The required significance level of findings will be 5%. If statistical tests are performed, they will be two-sided and nominal *p*-values will be presented.

For comparison of means (continuous variables), the paired t-test or the Wilcoxon rank sum test will be used as appropriate. For comparison of proportions (categorical variables), the Chi-squared test or Fisher's exact test will be used as appropriate.

Analyses will be carried out using IBM Corp. Released 2017. IBM SPSS Statistics for Windows, Version 25.0. Armonk, NY: IBM Corp.

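### With 20 subjects and an SD of 20 the two-sided 95% interval extends 8.8 points (z) or 9.4 points (t), not 8, so at that SD an observed 58% does not reach the 50% bound

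*Combined protocol and SAP*

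**What the plan says.** Under Sample Size Estimation, the combined protocol and SAP justifies 20 evaluable subjects by precision alone: "When the sample size is 20, a two-sided 95% confidence interval for a single mean will extend 8 from the observed mean". Two conditions are attached: "assuming that the standard deviation is known to be 20", and "the confidence interval is based on the large sample z statistic".

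Two consequences are drawn. The first is "If the expected rate is 58% the lower bound of the 95% confidence interval will be 50" (percent). The second is "A result of 58% will ensure with 95% level of confidence that the true percentage is not less than 50" (percent).

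The 50% figure is the target in the Study Hypothesis section and the comparison value for the primary endpoint under Efficacy Analysis, where a paired t-test or a signed rank test is named. General Considerations says that, where confidence limits are appropriate, "a two-sided 95% confidence interval will be constructed". It also makes any tests two-sided and sets significance at 5%.

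**The concern.** Every input needed to check the half-width is stated in one sentence, and the result does not follow from them. The plan subtracts the half-width from 58% and lands exactly on 50%, so any understatement of the half-width puts the true lower limit below the target.

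This section is the only sample size justification in the documents and the only place that says what observed result would support the hypothesis. With an SD near 20, an observed mean between 58% and about 59% would meet the statement in the sample size section but fail the two-sided interval and test in the analysis section. A reader would then have two conflicting accounts of whether the hypothesis was supported.

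**Working it through.** **Inputs, all from the combined protocol and SAP**
- n = 20, SD = 20 percentage points treated as known, two-sided 95%, z statistic, stated half-width 8, illustrative result 58% (Sample Size Estimation)
- Target 50% (Study Hypothesis)
- t-test or signed rank test against 50% (Efficacy Analysis, primary endpoint)
- Two-sided intervals and tests, 5% level (General Considerations)

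**1. The plan's own figure.** Half-width = z × SD/√n = 1.960 × 20/√20 = 1.960 × 4.472 = **8.77**. The stated 8 is not reproduced. Ordinary rounding would give 9.

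**2. What would give 8.**
- Sample size with z: n = (1.960 × 20/8)² = 24.01. At n = 24 the half-width is 8.002.
- Sample size with t: 27 is the first n with a half-width of 8 or less (7.91; n = 26 gives 8.08).
- SD at n = 20: 8 × √20/1.960 = 18.3 (z), or 8 × √20/2.093 = 17.1 (t).
- Confidence level: at n = 20 and SD 20, ±8 carries 92.6% two-sided confidence (z) or 91.0% (t).

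**3. The t version.** The SD will be estimated from the data, so the interval that matches the planned t-test uses t with 19 degrees of freedom: 2.093 × 4.472 = **9.36**.

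**4. Effect on the 58% statement, at n = 20 and SD 20**

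| | Two-sided 95%, z | Two-sided 95%, t | One-sided 95%, z | One-sided 95%, t |
|---|---|---|---|---|
| Half-width (distance to the bound) | 8.77 | 9.36 | 7.36 | 7.73 |
| Lower limit at observed 58% | 49.2 | 48.6 | 50.6 | 50.3 |
| Observed mean needed for a limit of 50 | 58.8 | 59.4 | 57.4 | 57.7 |

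The two-sided p-value against 50% at an observed 58% is 0.074 (z, statistic 8/4.472 = 1.79) or 0.090 (t).

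**5. Size of the error.** The correct half-width exceeds the stated one by 8.77/8 − 1 = 10% (z) or 9.36/8 − 1 = 17% (t). Taken against the correct values, the stated 8 is too small by 8.7% or 14.5%.

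**6. Other numbers of evaluable subjects.** If all 25 enrolled subjects were evaluable, the half-width would be 7.84 (z) or 8.26 (t). At the plan's own 25% dropout, 25 × 0.75 = 18.75 remain. With 18 or 19 subjects the z half-width is 9.2 or 9.0.

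**The case against.** The strongest reply is that the fault is small and does not touch the analysis. On the stated z method it is 0.77 points, and the primary interval and test will be computed from the data, so the planning figure never enters the inference. That is true, and it is why correcting the text is enough. The error still matters because the plan puts the bound exactly on the target.

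Other points, and what stands of each:

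- **One-sided reading.** The closing sentence of the section speaks of only one direction, and one-sided confidence at 58% is 96.3% (z) or 95.5% (t). Taken alone, that sentence can be defended. But the section derives it from an interval it calls two-sided, and General Considerations specifies two-sided intervals and tests.
- **A smaller SD or more subjects would rescue 58%.** This is correct. With 20 subjects and an observed SD of 17, the t half-width is 7.96; with 25 subjects and z it is 7.84. But the claim is made for n = 20 and SD 20, and the plan aims for at least 20 evaluable subjects, not 25.
- **The t figures are a separate matter.** Planning with z and analysing with t is a common approximation that the plan discloses. The arithmetic error proper is 8.77 against 8. The t figure is relevant because it is closer to what the analysis will produce. If the signed rank test is used instead, 59.4% is not its threshold.
- **Low probability of reaching the bound.** If 58% is read as the true mean, the chance that the lower limit exceeds 50 is about 43% (z) or 40% (t). Even a half-width of exactly 8 would give only 50% with z. This follows from planning on precision, and the plan claims no power. It is a reason to drop the word expected, but not part of the arithmetic error.

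**Conclusion.** The concern holds. On the plan's own inputs the half-width is 8.77, not 8, and no other section corrects it. At n = 20 and SD 20, an observed 58% has a two-sided 95% lower limit of 49.2% (z) or 48.6% (t), so it does not exclude a true mean reduction below 50%. The observed mean needed is 58.8% (z) or 59.4% (t).

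The conclusion rests on the stated n, SD and two-sided level. It would no longer apply at n = 20 if the observed SD were about 18.3 or less (z) or 17.1 or less (t). The stated 8 fits 24 to 25 subjects with z, close to the enrolment ceiling, but whether that is how it arose cannot be told from the documents.

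**What to change.** Rewrite the sample size statement and leave n as it is. Suggested text:

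*With 20 evaluable subjects and an SD of 20 percentage points, the two-sided 95% t-based confidence interval for the mean percentage reduction extends 9.4 points either side of the observed mean. If the observed SD is 20, an observed mean reduction of at least 59.4% is needed for the lower limit to reach 50%.*

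If the known-SD z formula is kept, the figures are 8.8 and 58.8%. In either case:

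- Refer to an observed mean, not an expected rate, so that the sentence is not read as a statement about the likely result or about power.
- Replace the closing sentence, which says that 58% ensures the conclusion, with the conditional statement above.

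The cost is wording in one section, with no change to enrolment, conduct or analysis. The stated precision and the required result become slightly less favourable.

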## **Efficacy Analysis**

### ***Primary endpoint***

The overall mean percentage reduction in AK lesion count performed by the investigator manually, confirmed and documented using photograph images taken at baseline and at 12 weeks follow-up visit calculated as the relative change from baseline at 12 weeks will be calculated along with 95% confidence interval.

The Paired T-test or Signed rank test for two means (paired observations) (as is appropriate) will be applied for testing the statistical significance of the percentage reduction in in actinic keratosis lesion count from baseline at week 12 (compared to 50%).

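### The sample-size section puts the expected mean in place of the observed mean: with a true mean of 58% the lower 95% limit reaches 50% in about 40–50% of trials, depending on the interval used, not with certainty

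*Combined protocol and SAP*

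**What the plan says.** The Study Hypothesis section sets the target to be tested: "Mean reduction in AKs lesion count 3 months after the final treatment will be at least 50" percent. The Sample Size Estimation section supports 20 evaluable subjects with a precision statement: "When the sample size is 20, a two-sided 95% confidence interval for a single mean will extend 8 from the observed mean". That width is said to rest on a z interval with an SD of 20 taken as known. The section then links the interval to the 50% target in two sentences:

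- The first concerns the expected value: "If the expected rate is 58% the lower bound of the 95% confidence interval will be 50" percent.
- The second concerns the observed value: "A result of 58% will ensure with 95% level of confidence that the true percentage is not less than 50" percent.

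Under Efficacy Analysis, the primary endpoint is reported with a 95% confidence interval and compared with 50%: "The Paired T-test or Signed rank test for two means (paired observations) (as is appropriate) will be applied for testing the statistical significance". General Considerations adds: "The required significance level of findings will be 5%. If statistical tests are performed, they will be two-sided". The documents state no power for this comparison.

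**The concern.** The two linking sentences use 58% in two different senses. In one it is the expected rate, a value assumed for the true mean before the trial. In the other it is a result, the mean actually observed. The interval was introduced as extending from the observed mean, so only the second sense fits it. Putting the expected value in that place leaves out sampling variation: a device whose true mean reduction is exactly 58% will give observed means on both sides of 58%.

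At stake is the justification for 20 subjects. The section reads as if the 50% target will be met should the device perform as expected. The probability of that is not stated, and it is far from certainty.

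**Working it through.** **Inputs.** From Sample Size Estimation: n = 20, SD = 20 percentage points (treated as known), two-sided 95% z interval, expected mean 58%. From Study Hypothesis and Efficacy Analysis: threshold 50%. From Efficacy Analysis and General Considerations: t-test or signed rank test, two-sided 5%.

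**Step 1. The plan's own figures.** 58 − 8 = 50, so the subtraction is right if the half-width is 8 and the observed mean is 58. The half-width does not follow from the inputs:

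- SE = 20/√20 = 4.472.
- z half-width = 1.960 × 4.472 = 8.77.
- t half-width (19 df, observed SD 20) = 2.093 × 4.472 = 9.36.
- n for a z half-width of 8 = (1.960 × 20/8)² = 24.01, not 20.

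**Step 2. 58% as the observed result, n = 20.** The lower limit is 58 − 8.77 = 49.23% (z) or 58 − 9.36 = 48.64% (t). The two-sided z p-value against 50% is 0.074.

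**Step 3. 58% as the true mean.** The lower limit reaches 50% when the observed mean is at least 50 plus the half-width.

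| Basis (true mean 58%, SD 20) | Observed mean needed | Probability |
|---|---|---|
| Plan's stated half-width of 8 | 58.0% | 50% |
| z interval, n = 20 | 58.8% | 43.2% |
| t interval, n = 20 | 59.4% if observed SD is 20 | 39.7% |

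- Row 1: the observed mean is distributed symmetrically about 58%, so it falls below 58% half the time. This isolates the expected-for-observed error.
- Row 2: Φ(8/4.472 − 1.960) = Φ(−0.171) = 0.432. The fall from 50% to 43% comes from correcting the half-width.
- Row 3: noncentral t, 19 df, noncentrality 8/4.472 = 1.789, giving 0.397. The fall from 43% to 40% comes from moving from z to t, which matches the t-test option in the primary analysis.

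Simulation of 400,000 trials at n = 20 gave 43.3% (z) and 39.8% (t).

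**Step 4. True mean needed for 80% probability at n = 20.** With z: 50 + (1.960 + 0.842) × 4.472 = 62.5%. With t: 63.2%.

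**Step 5. Sensitivity.**

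- SD (t, n = 20, true mean 58%): about 62% at SD 15, 51.5% at SD 17, 40% at SD 20 and 27% at SD 25. The values other than 20 are assumptions, made because the plan gives no source for its SD.
- All 25 enrolled subjects evaluable, SD 20: 51.6% (z) or 48.4% (t).

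**The case against.** The strongest defence is that this is a precision calculation and claims no power. The section speaks first of the observed mean and last of a result of 58%, so the sentence between them can be read as: if the result comes out as expected, the lower limit is 50%. On that reading no probability of success is asserted. This is fair as an account of how the sentence came about, but it does not rescue the text. Step 2 shows that an observed 58% with 20 subjects and SD 20 gives a two-sided lower limit below 50% on either interval.

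Read alone, the last sentence could be defended as a one-sided 95% statement: the one-sided z half-width is 7.36, giving a lower limit of 50.64%. However, the section specifies a two-sided interval and General Considerations specifies two-sided tests. Even one-sided, a true mean of 58% succeeds in only 56% (z) or 53% (t) of trials.

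Two stronger readings are tempting, and the documents do not support them:

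- A reader might infer that a device performing as expected is always more likely to miss the target than to meet it. That holds at n = 20 and SD 20 on the z and t intervals. It does not hold at the stated half-width of 8 (an even chance), with z if all 25 subjects are evaluable (51.6%), or with t at n = 20 if the SD is 17 (51.5%).
- A reader might infer that a miss would be taken as evidence against the device. The documents do not say how a lower limit below 50% will be interpreted.

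It is also fair to object that a bare figure of 40% mixes three things: the expected-for-observed substitution, the half-width error and the change from z to t. The table therefore separates them.

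**Conclusion.** Wrong as written. An expected mean of 58% does not imply a lower limit of 50%. The substitution alone reduces the implied certainty to 50%; with the half-width corrected at 20 subjects, the probability is 43% (z) or 40% (t). Taking 58% as the observed result does not restore the claim for the two-sided interval that the plan specifies.

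These figures assume a true mean of 58%, an SD of 20, approximately normal data for the t calculation, and 20 evaluable subjects. They do not cover the signed rank option. The SD matters most: across assumed SDs of 15 to 25 the t-based probability runs from about 62% to 27%, and nowhere in that range is it close to certain. The planned analysis can still be carried out; what fails is the stated justification for its size.

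**What to change.** Keep the sample size. Replace the two linking sentences in Sample Size Estimation with:

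> With 20 evaluable subjects and an observed SD of 20, the observed mean must be at least 59.4% for the lower limit of the two-sided 95% t interval to reach 50% (58.8% with a known-SD z interval). If the true mean is 58% and the SD is 20, this occurs with probability of about 40% (t) or 43% (z); it reaches 80% if the true mean is about 63%. The probability depends on the assumed SD (t, n = 20: about 62% at SD 15 and 27% at SD 25).

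At the same time, correct the half-width of 8 in the opening sentence to 8.77 (z), or to 9.36 if the section moves to t.

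The cost is a few sentences, with no extra subjects or visits and no change of analysis. The downside is that the stated operating characteristic is less favourable. For context, 80% probability at a true mean of 58% and SD 20 would take about 50 (z) or 52 (t) evaluable subjects; the wording change does not require that increase.

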### REFERENCES :

To overcome the expected dropout rate of up to 25% we will recruit up to 25 subjects.

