### Study Synopsis

Protocol #	CLN 0827
Study Title	Evaluation of the Efficacy and Safety of a thermal fractional skin treatment system (Tixel®) for the treatment of facial and/or scalp actinic keratoses
Study Device	Tixel C (by Novoxel)
Device Description	Tixel technology is a thermal fractional skin treatment system powered by Thermo-Mechanical Action technology. Tixel employs a hot titanium tip which transfers direct heat to the skin. The proprietary tip is constructed of biocompatible temperature resistant titanium alloy cover mounted on gold plated copper base. The tip consists of an array of tiny pyramids which are heated to a temperature of 400°C. The apex of the pyramids transfers thermal energy to skin by very brief controlled contact time.
Study Design and Duration	
Single-center, Prospective, Open Label, with Before-After Study Design.
 
Up to 25 subjects will be enrolled to the study to provide at least 20 evaluable subjects. Subjects will be examined to determine the severity and extent of actinic keratoses.
 
All subjects will undergo 1-3 treatments (determined by the investigator assessment), 3-4 weeks apart.
 
Follow-up visits will be performed after the last treatment visit: 4 weeks (±7 days) and 12 weeks (±7 days).
 
The inclusion criteria would be mild to moderate thickness confluent actinic keratoses located to scalp and/or face.
 
Each subject will participate in the study for up to 20 weeks.
 
Total study duration is estimated to be up to 12 months from enrollment of the first subject until last subject visit (including FUs).

Investigational Treatment	This is a non-invasive thermo-mechanical treatment to the scalp and/or face using the Tixel technology. The handpiece will be pressed gently onto the scalp/facial skin while transferring heat in a predetermined setting.
Objectives	
Primary objective
 
To evaluate the efficacy of the Tixel technology (device) for the treatment of facial and/or scalp actinic keratoses.
 
Secondary objectives
 
 
• To evaluate procedure-related adverse reactions.
 
• To evaluate Subject's subjective downtime assessment.
 
• To Evaluate the pain of the treatment.
 
• To Evaluate the subject's satisfaction.
 

Study synopsis.

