### **Per-Protocol (PP)**

The per-protocol analysis set (PP) will consist of only patients who received the full treatment session and have photos from the 3-month follow up visit.

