### **Statistical Analysis of Analysis Sets**

The FAS analysis set will serve as the main set for safety assessments. The primary efficacy assessment will be performed on the PP analysis set and as supportive analysis, on the FAS.

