#### **Handling of Missing Data**

Missing data will not be imputed.

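### Enrolling 25 subjects covers drop-out of up to 20%, not the stated 25%: a sixth loss, still inside the allowance, leaves 19 evaluable subjects instead of 20

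*Combined protocol and SAP*

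**What the plan says.** All references are to the combined protocol and SAP.

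- The Study Synopsis (Study Design and Duration, repeated under Study Population) sets both the cap and the target: "Up to 25 subjects will be enrolled to the study to provide at least 20 evaluable subjects".
- Sample Size Estimation takes 20 as the analysed number: "When the sample size is 20, a two-sided 95% confidence interval for a single mean will extend 8 from the observed mean". It treats an SD of 20 as a known value.
- The drop-out allowance is a single sentence printed under the REFERENCES heading that follows: "To overcome the expected dropout rate of up to 25% we will recruit up to 25 subjects".
- Statistical Analysis of Analysis Sets makes the per-protocol set primary: "The primary efficacy assessment will be performed on the PP analysis set". The full analysis set is supportive.
- Per-Protocol (PP) admits "only patients who received the full treatment session and have photos from the 3-month follow up visit".
- Handling of Missing Data: "Missing data will not be imputed".

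The document gives no replacement rule, no enrolment above 25, and no calculation linking 20 to 25.

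**The concern.** A drop-out allowance has to work at its stated ceiling. Here the cap of 25, the ceiling of 25% and the target of 20 fit together over only part of that range. The drop-out sentence is the plan's only stated reason for choosing 25.

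Losses fall directly on the primary estimate. A subject without photographs from the 3-month visit is outside the per-protocol set. With no imputation, a subject who has no week-12 count also adds nothing to the week-12 mean in the supportive full-analysis-set result. The number retained is therefore the number on which the precision statement rests, and the plan says that number will not fall below 20.

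**Working it through.** **Inputs.** Maximum enrolment 25 and evaluable target 20 (Study Synopsis); drop-out of up to 25% (sentence under REFERENCES); SD 20, two-sided 95% interval, expected mean reduction 58%, threshold 50% (Sample Size Estimation).

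**1. Reproducing the plan's figure.** Multiplying the target by one plus the drop-out rate gives 20 × (1 + 0.25) = 25, exactly the stated number. Dividing by the proportion retained, which is what keeps 20 after the loss, gives 20 / (1 − 0.25) = 26.67, rounded up to 27. The division returns 25 only at a rate of 1 − 20/25 = 20%.

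**2. Forward check from 25 enrolled.** At the ceiling, 25 × 0.75 = 18.75. In whole subjects:

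| Lost | Share of 25 | Remaining | Within the 25% ceiling? | 20 retained? |
|---|---|---|---|---|
| 4 | 16% | 21 | yes | yes |
| 5 | 20% | 20 | yes | yes |
| 6 | 24% | 19 | yes | no |
| 7 | 28% | 18 | no | no |

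Only six losses break the promise while staying inside the allowance.

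**3. Smallest cap that works in whole subjects.** With 26 enrolled, 6 losses are 6/26 = 23.1% and leave 20; 7 losses are 7/26 = 26.9%, above the ceiling. So 26 just suffices on a whole-subject count, and 27 by the usual formula. Neither route gives 25.

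**4. Effect on precision, SD 20.** Half-width = 1.96 × 20/√n (z) or t(0.975, n − 1) × 20/√n (t). The mean needed is 50 plus the half-width.

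| Evaluable | Half-width, z | Half-width, t | Mean needed, z | Mean needed, t |
|---|---|---|---|---|
| 20 | 8.77 | 9.36 | 58.8% | 59.4% |
| 19 | 8.99 | 9.64 | 59.0% | 59.6% |

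If the true mean is 58%, the chance that the lower t-based limit exceeds 50% (noncentral t) is 39.7% with 20 subjects and 37.9% with 19.

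**5. Chance of keeping 20.** The plan gives no drop-out model. Assuming that each of 25 subjects drops out independently, the probability of retaining 20 or more is 0.38 at a rate of 25% and 0.62 at 20%.

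The z half-width at n = 20 is 8.77, not the 8 stated in Sample Size Estimation. That is a separate error and none of it is counted here.

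**The case against.** The strongest reply is that the drop-out figure is a ceiling, not a forecast. From 0 to 5 losses everything agrees, and only one whole-subject outcome within the allowance fails, by one subject. That is correct and it limits the size of the problem. It does not make the sentence true, because the sentence claims cover up to the ceiling. Since 25 is itself a maximum, enrolling fewer would make the shortfall larger.

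Two links are also inferred. The document does not define an evaluable subject, so equating it with membership of the per-protocol set is a reasonable reading rather than a stated one. Nor does it state the base of the 25%: five extra subjects on 20 is 5/20 = 25%. A drop-out rate, however, is ordinarily a share of those enrolled, and the wording gives no sign of another base.

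Finally, correcting the half-width in Sample Size Estimation could overtake this point. A z half-width of 8 at SD 20 needs (1.96 × 20/8)² = 24.01 subjects. With a target of 24, a cap of 25 would leave room for one loss. This is a good reason to settle both points together, but correcting the half-width alone would not make the drop-out sentence consistent.

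**Conclusion.** The inconsistency is real and follows from the plan's own figures. Twenty-five enrolled subjects retain 20 only when realised drop-out is 20% or less; between 20% and the stated 25%, they leave 19.

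The consequence is small: one evaluable subject, 0.2 to 0.3 points of half-width, and just under 2 percentage points in the chance of clearing 50% at a true mean of 58%. It would not by itself change how the trial is interpreted. It should still be corrected, because the plan states a retained sample that the design does not guarantee.

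The conclusion assumes that all 25 are enrolled, that drop-out is a share of those enrolled, and that a lost subject has no week-12 count. The precision figures also assume the plan's SD of 20.

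**What to change.** **Preferred:** keep the cap of 25 and replace the drop-out sentence with: *Enrolling 25 subjects allows for up to 20% drop-out while retaining 20 evaluable subjects.* This agrees with the synopsis as it stands. It costs one sentence, with no extra recruits and no change to endpoint, analysis set or test. The downside is a less generous stated allowance. It describes what the cap can absorb; it does not make drop-out less likely.

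**If 25% is the sponsor's genuine expectation,** one of these is needed instead:

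- Raise the cap to 27 (26 is the whole-subject minimum) in the synopsis and in the drop-out sentence, at the cost of one or two more recruits.
- Keep 25 enrolled and state that as few as 19 evaluable subjects may remain, with a 95% half-width of 9.0 (z) or 9.6 (t) at SD 20. The target then becomes 19 in both synopsis entries. Sample Size Estimation must change too, because it still plans on 20 subjects and a half-width of 8.

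Whichever is chosen, agree it together with the correction of the half-width in Sample Size Estimation. If that correction raises the evaluable target, the enrolment cap and the drop-out allowance must be recalculated from the new target.
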